CLINICAL TRAIL PROTOCOL

Protocol Title: Immunogenicity and Safety of a Quadrivalent Influenza Vaccine: a Randomized, Blind, a Phase III Clinical Trial.

Collaborators: Jiangsu Center for Disease Control and Prevention

Sponsor: Shanghai Institute of Biological Products

Document Date: October 12, 2018

BACKGROUND INFORMATION

Influenza is an acute, highly infectious and rapid respiratory infectious disease caused by the influenza virus, which is one of the important causes of human death. Influenza viruses are classified into three subtypes A, B and C. Influenza A and influenza B viruses, particularly influenza A viruses, are prevalent in the population and in the form of seasonal influenza, while influenza C viruses are uncommon and cause only mild symptoms. Influenza A viruses can be divided into different subtypes according to the two surface antigens hemagglutinin (HA) and neuraminidase (NA) of the virus.

Currently, influenza A viruses causing seasonal influenza are mainly influenza viruses of the H1N1 subtype and H3N2 subtype. The investigation showed that the B/Victoria lineage dominated the B/Yamagata strain from 1940 to 1980, while the B/Yamagata lineage dominated from 1987 to 1989. But since 2001, two different strains of B influenza virus B/Victoria/2/87-like and B/Yamagata/16/88-like have been circulating at the same time.

In February 2012, the world health organization (who) for the first time suggested that the seasonal flu vaccine should contain two kinds of B lineage strain proposal. Since 2013-2014, flu season in the northern hemisphere, WHO began to recommend quadrivalent vaccine, to add another subtype B influenza virus in trivalent vaccine, in order to achieve better protection effect. In recent years, the development of quadrivalent influenza vaccine has become an important trend of influenza vaccine.

STUDY OBJECT

First objects:

To evaluate the immunogenicity of quadrivalent influenza vaccine 30 days in healthy population years aged 3 years and above, according to investigate antibodies at day 30 after one inoculation

Secondary objects:

To evaluate the safety of quadrivalent influenza vaccine 30 days in healthy population years aged 3 years and above, according to investigate occurrence of adverse events for 30 days after one inoculation.

To prove conversion rate and geometric mean titer (GMT) of quadrivalent influenza vaccine being non-inferior for shared strains to trivalent influenza vaccines.

STUDY DESIGN

The safety evaluation of each group will be divided into three stages. From the first dose inoculation to day 7 after inoculation; From the first dose inoculation to day 21 after inoculation; From the second dose inoculation to day 30 after the second dose inoculation. The first stage is the basis for the follow-up group of the same vaccine, and will be carried out under blind. The latter two stages are the basis for evaluation of vaccine safety, and will be carried out under unblind. If each evaluation is not found level 4 local and systemic adverse reactions associated with vaccine and the total incidence rate of level 3 of local and systemic adverse reactions and abnormal laboratory test which associated with the vaccination is lower than 15%, that the vaccine will be acceptable safety.

EVALUATION CRITERIA OF IMMUNOGENICITY

If seroconversion rate is higher than 40%, the antibody protection rate higher than 70%, GMI more than 2.5 times, the vaccine will be acceptable immunogenicity.

STUDY STATUS

Record Verification: October 2018

Study Start: November 2018

Primary Completion: March 2019

Study Completion: June 2019

ELIGIBILITY

Inclusion Criteria:

Over the age of three years, healthy population

Subjects/ (and the guardian) informed consent, voluntarily participated and signed the

informed consent form, with the ability to use thermometers, scales and to fill in diary cards as required

To comply with the requirements of clinical trial program

Temperature≤37.0°C on day of enrollment

Exclusion Criteria:

A history of influenza virus infection or suspected infection Abnormal blood routine, blood biochemistry and urine routine examination indexes in last three months

Any prior administration of influenza vaccine in last six months

Allergy to any component in the vaccine, especially for egg allergy

Allergy history of any previous vaccination or drug

Acute episodes of chronic illness or acute illness on the day of vaccination

Received a live vaccine within fourteen days prior to receiving the vaccine, or received a subunit or inactivated vaccine within seven days

Congenital or acquired immune deficiencies, or treatment with immunosuppressive agents, such as long-term treatment with systemic corticosteroids

Suffering from severe chronic diseases (such as Down's syndrome, diabetes, sickleemia or neurological disorders, Green's Barre syndrome)

Asthma, required urgent treatment in last two years

The blood products were received prior to the acceptance of the vaccine

Known or suspected of respiratory disease, acute infection or chronic disease active period, HIV infection, cardiovascular disease, severe hypertension, malignant tumor during treatment, skin diseases

History of epilepsy, convulsions, or a family history of psychosis

Abnormal coagulation function (such as coagulation factor deficiency, coagulation disorders, platelet abnormalities), or obvious bruising or coagulopathy

Plan to move or leave the area for an extended period of time before the end of the study

Under anti-tb treatment

Any prior administration of other research medicine/vaccine in last one month

Women are pregnant or in the near future planned pregnancy or pregnancy test positive

DATA STATISTICS

Statistics analysis of immunogenicity

The prevaccination and postvaccination geometric mean of antibody and its 95% confidence interval (confidence interval, CI) will be described. The postvaccination serum conversion rate and protection rate of antibody and their 95% CI will be described.

Comparisons will be conducted to evaluate differences in response between study groups using a χ^2 test or Fisher's exact test to compare to the difference of serum conversion rate and protection rate. Statistical significance will be considered at a level of $\alpha = 0.05$ and all tests will be 2-sided.

If serum HI antibody conversion rate is more than 40%; protection rate more than 70%; GMI more than 2.5 folds, the immunogenicity will reach the design requirements.

Statistics analysis of safety

After the first dose inoculation and the second dose inoculation, the number of adverse reactions (rate), number of cases and adverse reaction grade were recorded.

The number of adverse events after inoculation will be described.

Comparisons will be conducted to evaluate differences in response between study groups using a χ^2 test or Fisher's exact test to compare to the difference of adverse events rate. Statistical significance will be considered at a level of $\alpha = 0.05$ and all tests will be 2-sided.

Comparison of compliance

The rate of expulsion and the rate of drug combination will be described.

Comparisons will be conducted to evaluate differences in response between study groups using a χ^2 test or Fisher's exact test to compare to the difference of the rate of expulsion and the rate of drug combination. Statistical significance will be considered at a level of $\alpha = 0.05$ and all tests will be 2-sided.

APPENDIX I. GRADING STANDARDS FOR SEVERITY OF SAFETY INFORMATION

The Event of clinical response and laboratory abnormalities after vaccination is judged by the China State Food and Drug Administration on "Guidelines for the classification of adverse events in vaccine clinical trials".

Grading of Local Adverse Events

Local Adverse Reactions	Mild (Grade 1)	Moderate (Grade 2)	Severe (Grade 3)	Potential Life Threatened (Grade 4)
Pain	Do not affect activity	Influence activities or multiple use of non-narcotic analgesics	Affect daily activities or multiple use of narcotic analgesics	Emergency or hospitalization
Induration	<15 mm	15-30 mm	>30 mm	Gangrene or exfoliative dermatitis
Redness	<15 mm	15-30 mm	>30 mm	Gangrene or exfoliative dermatitis
Swelling	<15 mm and does not affect activity	15-30 mm or affect activity	>30 mm or limit daily activity	Gangrene
Rash (injection site)	<15 mm	15-30 mm	>30 mm	
Itching	Injection site itching	Injection of moderate itching	Overall Itching	

Grading of Systemic Adverse Events

Systemic Adverse Reactions	Mild (Grade 1)	Moderate (Grade 2)	Severe (Grade 3)	Potential Life Threatened (Grade 4)
Fever	37.1-37.5°C	37.6-39.0°C	>39.0°C	
Headache	No activity, no treatment	Transient, slightly affected activity requiring treatment (multiple use of non-narcotic analgesics)	Severe effects on daily activities, initial anesthetic response	Refractory, repeated anesthetic treatment. Emergency or hospitalization
Fatigue and fatigue	The normal activity is less than 48 hours, and it did not affect the activity	Normal activity decreased from 20% to 50% > 48 hours, slightly affecting activities	Normal activity decreased by more than 50%, seriously affecting daily activities, unable to work	Unable to take care of oneself, emergency or hospitalization
Nausea and vomiting	1~2 times per 24 hours, intake is normal and does not affect the activity	2 ~ 5 times per 24 hours, intake is significantly reduced, or limited activity	> 6 times within 24 hours, no obvious intake, the need for intravenous infusion	requires hospitalization or other nutrition because of hypotension, shock
Diarrhea	Mild or transient, 2 ~ 3 stools per day or mild diarrhea lasting for less than 1 weeks	Moderate or persistent, 4~5 times per day, or more than 1 week diarrhea	> 6 times of water stool per day, or blood diarrhea, orthostatic hypotension	Hypotension shock requiring hospitalization
Myalgia	Not affecting daily activities	Muscle tenderness at the non injection site slightly affects daily activity	Severe muscle tenderness seriously affects daily activities	The symptoms are obvious, muscle necrosis, emergency or hospitalization

Cough	Transient, without treatment	Persistent cough, effective treatment	Paroxysmal cough, treatment can not control	Emergency or hospitalization
Allergy	Pruritus without skin rash	Local urticaria	Extensive urticaria, vascular edema	Severe allergy
Other adverse or clinical adverse reactions (based on the corresponding criteria)	Do not affect activities	Slightly affects activities without drug treatment	Serious impact on daily activities requires drug treatment	

APPENDIX II . THE RELATIONSHIP BETWEEN ADVERSE EVENTS AND TRIAL VACCINES

Absolutely unrelated: Because of other factors lead to adverse events, there is evidence that adverse events are caused by other causes, not related to vaccination.

Possible unrelated: Adverse events probable be caused by other factors, such as the clinical status of the subjects, other treatment or concomitant medication, inconsistent with the known adverse reactions of vaccination.

Quite possible related: Adverse events are consistent with known information of vaccine, and there is a causal relationship with the vaccine, not by other factors, such as the clinical status of the subjects, or other treatment with medication.

Possible related: Adverse events are consistent with known information of vaccine, and there is a causal relationship with the vaccine, not by other factors, such as the clinical status of the subjects, or other treatment with medication.

Related: Adverse events are consistent with known information of vaccine, and there is a causal relationship with the vaccine, not by other factors, such as the clinical status of the subjects, or other treatment with medication. In addition, adverse events will be repeated when subjects are tested with the vaccine.

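### The safety pass rule counts only vaccine-associated events, but the causality definitions never let a typical reaction with an unproven other cause count as associated

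*Combined protocol and SAP*

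**What the plan says.** The pass rule stands in the protocol under Evaluation Criteria of Safety. Its first limb and the start of its second read "If each evaluation is not found level 4 local and systemic adverse reactions associated with vaccine and the total incidence rate of level 3". The second limb covers local and systemic reactions and abnormal laboratory tests, and ends "which associated with the vaccination is lower than 15" (per cent). Both limbs therefore turn on a causality judgement.

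Appendix II is the only causality scale in the documents. It has five levels:

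- *Absolutely unrelated*: "Absolutely unrelated: Because of other factors lead to adverse events, there is evidence that adverse events are caused by other causes".
- *Possible unrelated*: "Possible unrelated: Adverse events probable be caused by other factors", with the examples ending "other treatment or concomitant medication, inconsistent with the known adverse reactions of vaccination".
- *Quite possible related*: "Quite possible related: Adverse events are consistent with known information of vaccine, and there is a causal relationship with the vaccine, not by other" factors.
- *Possible related*: the same definition as the level above, "possible related: Adverse events are consistent with known information of vaccine, and there is a causal relationship with the vaccine, not by other factors".
- *Related*: the same definition again, with the addition that "adverse events will be repeated when subjects are tested with the vaccine".

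No section states which levels count as associated. Under Statistics analysis of safety, the grade of adverse reactions is recorded and adverse event rates are compared between groups.

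**The concern.** A causality scale has to place the uncertain cases, because the clear ones cause little dispute. Here all three related levels require that other factors are not the cause, so the scale has no related level for an event that fits the vaccine but might have another explanation. One example is a fever or cough, both on the solicited list, in a participant who may also have an unrelated infection.

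The verdict is an absolute threshold, not a comparison with the control vaccines. An event that meets no definition is placed by the assessor's judgement, and an event pushed into an unrelated level leaves the count. One Grade 4 event of this kind can settle the first limb. In the second limb, such events can decide which side of 15% the rate falls on. The planned between-group comparison is only a partial safeguard: it is not stated by grade and does not feed the pass rule.

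**Working it through.** The plan gives no figure to reproduce here: it states no expected event rate and no sample size. The check is therefore a comparison of definitions, followed by the conditions under which the verdict could move.

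**1. Duplication.** The definitions of *Quite possible related* and *Possible related* are identical, at 35 words each. The definition of *Related* opens with the same 35 words.

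**2. Coverage.** Cross two features that the definitions use: whether the event is consistent with known reactions (2 states), and the status of another cause (proven, probable, plausible but unproven, excluded: 4 states). This gives 2 × 4 = 8 profiles, with no recurrence observed. The split between probable and plausible is a device of this check; Appendix II does not define it. Two words in *Possible unrelated* can be read strictly or loosely: *inconsistent* as a requirement or only a comment, and *probable* as written or as *may*. AU = *Absolutely unrelated*, PU = *Possible unrelated*, QPR = *Quite possible related*, PR = *Possible related*.

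| Event; other cause | Both strict | *Inconsistent* loose | *Probable* loose | Both loose |
|---|---|---|---|---|
| Consistent; proven | AU | AU | AU | AU |
| Consistent; probable | none | PU | none | PU |
| Consistent; plausible | none | none | none | PU |
| Consistent; excluded | QPR and PR | QPR and PR | QPR and PR | QPR and PR |
| Inconsistent; proven | AU | AU | AU | AU |
| Inconsistent; probable | PU | PU | PU | PU |
| Inconsistent; plausible | none | none | PU | PU |
| Inconsistent; excluded | none | none | none | none |
| Profiles meeting none / one / two levels | 4 / 3 / 1 | 3 / 4 / 1 | 3 / 4 / 1 | 1 / 6 / 1 |

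Two rows matter. *Consistent; plausible* is unplaced on three readings and *Possible unrelated* on the fourth, so it never meets a related level. *Inconsistent; excluded*, which is what a new reaction would look like, is unplaced on all four. These are counts of profiles, not shares of events.

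**3. When the verdict can move.** Let c be the rate of clearly related Grade 3 events, laboratory abnormalities included, and u the rate of events whose placement is open. The second limb depends on placement only if c < 15% ≤ c + u. The first limb depends on it only if no clearly related Grade 4 event occurs and at least one open one does.

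**4. Illustration with assumed rates.** None of these rates is in the documents. If the crude Grade 3 rate is r and a share s is left out as not associated, the counted rate is r × (1 − s).

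| r | s = 10% | s = 20% | s = 30% |
|---|---|---|---|
| 12% | 10.8%, pass | 9.6%, pass | 8.4%, pass |
| 16% | 14.4%, pass | 12.8%, pass | 11.2%, pass |
| 18% | 16.2%, fail | 14.4%, pass | 12.6%, pass |
| 20% | 18.0%, fail | 16.0%, fail | 14.0%, pass |

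With nothing left out, the last three rows fail. At 12% the placement is irrelevant.

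**5. A smaller gap in Appendix I.** By count alone, Grade 2 ends at 5 episodes for both vomiting and diarrhea, and Grade 3 starts above 6. Exactly 6 episodes has no grade by count, at the boundary that decides entry to the second limb.

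**The case against.** The strongest reply is that the level names do the work the definitions fail to do. Two levels are named unrelated and three related, so a reader can infer the split. That largely stands: the missing statement of which levels count is a small omission. It also disposes of one tempting reading, that the duplicated definition by itself makes the verdict indeterminate. Both duplicated levels carry the name related, so choosing between them cannot change pass or fail.

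A second reply is that *probable* in *Possible unrelated* may be loose English for *may*. If *inconsistent* is also only a comment, every consistent event has a level. This is correct, as the last column of the grid shows, but it does not rescue the rule. The uncertain event then goes to an unrelated level and drops out of the count, and the new reaction with other causes excluded is still unplaced.

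A reader might also infer that causality will be judged with knowledge of the vaccine group, since the two later stages, named as the basis for the safety evaluation, are carried out unblinded. The documents do not say so. The rule applies to each evaluation, including the blinded first stage, which covers the 7-day systematic observation, and no text says when an individual event's level is assigned. The supportable statement is only that the plan does not fix causality before unblinding.

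The duplication may be a translation or copying slip, but it stands in the current text. On the Appendix I gap, other criteria in the same cells or the cited national guideline may settle some cases.

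**Conclusion.** The concern holds as a defect in a stated rule. The definitions give no route by which a vaccine-consistent event with a plausible, unproven other cause counts as associated, and no level for an unfamiliar reaction with other causes excluded. The first conclusion holds on each of the four readings tried, and so does the second. Both assume that Appendix II is the scale meant by the pass rule and that the three levels named related are those counted.

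The size of the effect cannot be estimated. It is confined to trials with no clearly related Grade 4 event but an open one, or with a Grade 3 rate near 15%. The direction is also not fixed. Unplaced events may be assigned either way, whereas the loosest reading removes the uncertain consistent events from the count. It would go too far to conclude that the plan favours the vaccine, or that half of all events cannot be classified. Safety is a secondary objective and the primary immunogenicity evaluation is untouched. The change should be made because it is cheap and makes the pass rule less open to judgement.

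**What to change.** 1. Appendix II: reword the five levels so that they are distinct and exhaustive.
   - *Absolutely unrelated*: another cause shown by evidence.
   - *Possible unrelated*: inconsistent with known reactions, and another cause probable or plausible.
   - *Possible related*: consistent with known reactions, with another cause neither proven nor excluded; or inconsistent, with other causes excluded and no recurrence observed, so that a new reaction is not dropped from the rule.
   - *Quite possible related*: consistent, other causes excluded, no recurrence observed.
   - *Related*: other causes excluded and recurrence observed, whether or not the reaction was known before.

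   In the order listed, the first four levels take 2 + 2 + 3 + 1 = 8 of the 8 profiles without recurrence, each exactly once. With recurrence observed, the two profiles with other causes excluded move to *Related* and the other six keep their level, so all 16 are placed once.
2. Evaluation Criteria of Safety: state that the three levels named related count as associated, for reactions and laboratory abnormalities alike, and that each event's level is assigned before unblinding.
3. Statistics analysis of safety: report Grade 3 and Grade 4 rates by group regardless of causality, beside the related rates.
4. Appendix I: reconcile the vomiting and diarrhea count bands with the cited guideline so that each count has one grade. No cut-off is proposed here.

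The cost is wording, one extra table and re-briefing of assessors. The related-event rate may look less favourable, by an amount the documents do not allow to be estimated.
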